5.2 Trial Treatment(s)

The investigator shall take responsibility for and shall take all steps to maintain appropriate records and ensure appropriate supply, storage, handling, distribution, and usage of trial treatments in accordance with the protocol and any applicable laws and regulations.

5.2.1 Therapeutic regimen Selection: TPS stimulation protocols

20 min stimulation with a maximum of 6,000 pulses and maximum of 0.25 mJ/mm² per session. 6 Sessions in 2 weeks per treatment period followed with a single stimulation session every 2 months (2 additional sessions by month 2 and 4).

5.2.2 Timing of Therapeutic Regimen Administration

The treatment will be administered in the first 4 weeks after randomization with a duration of 2 weeks for the first period. Then, single stimulation sessions will be conducted every 2 months, which means 2 additional sessions (month 2 and 4).

5.2.3 Trial Blinding/Masking

Patient and physician will be blinded. The sham reproduces the patient experience of the TPS treatment (mainly the sound produce by the stimulator). The treating researcher will be unaware of the patient allocation. An independent investigator informed of the therapeutic arm will prepare the device to administer treating stimulation or sham and will record such assignment for each treating visit in a secured file not available for the treating researcher.

5.3 Randomization

Treatment allocation/randomization will occur centrally using an interactive voice response system / integrated web response system (IVRS/IWRS). There are 2 treatment arms: active TPS and sham. Subjects will be assigned randomly in a 1:1 ratio to either TPS or sham.

5.4 Stratification

No randomization stratification is considered in this study

5.5 Concomitant Treatments (Allowed)

Patients will be allowed to take their therapy prescribed for ALS and any other comorbidity. Treatments specifically prohibited in the exclusion criteria are not allowed during the ongoing study. If there is a clinical indication for any treatment specifically prohibited during the trial, discontinuation from trial therapy may be required. The investigator should discuss any questions regarding this with the Principal Investigator. The final decision on any supportive therapy rests with the investigator and/or the subject's primary physician. However, the decision to continue the subject on trial therapy requires the mutual agreement of the investigator and the subject.

5.6 Rescue Treatments & Supportive Care

No rescue or supportive treatments are specified to be used in this trial.

5.7 Diet/Activity/Other Considerations

Not required.

5.7.1 Diet

Subjects should maintain their usual diet throughout the duration of the trial.

5.7.2 Use of Alcohol, Caffeine, and Tobacco

The site should advise subjects that alcohol should NOT be consumed during the study. The site should advise subjects to limit their alcohol intake as follows:

Refrain from consuming any alcohol for at least 24 hours prior to the study.

The site should advise subjects to limit their caffeine consumption as follows:

Limit their daily caffeine consumption to ≤600 mg caffeine. (See Appendix 12.7 for additional guidance on caffeine products and content.). In addition, caffeinated products should not be consumed until after completion of all procedures at the visit.

The site should advise subjects to limit their tobacco use as follows:

Refrain from the equivalent of >15 cigarettes a day during the study, and

Refrain from smoking during the study

5.7.3 Activity

NA

5.8 Subject Withdrawal/Discontinuation Criteria

Subjects may withdraw consent at any time for any reason or be dropped from the trial at the discretion of the investigator should any untoward effect occur. In addition, a subject may be withdrawn by the investigator if enrollment into the trial is inappropriate, the trial plan is violated, or for administrative and/or other safety reasons. Specific details regarding discontinuation or withdrawal procedures are provided in Section 7.1.4 – Other Procedures.

[Table 2](#) provides reasons why a subject must be discontinued from treatment but may continue to be monitored in the trial, as well as reasons why a subject must be discontinued from treatment and the trial.

Table 2 Discontinuation Scenarios

Reason for Discontinuation Scenario	Action
The subject or legal representative (such as a parent or legal guardian) withdraws consent.	Discontinuation from Treatment and Trial
The subject has a medical condition or personal circumstance which, in the opinion of the investigator, places the subject at unnecessary risk through continued participation in the trial or does not allow the subject to adhere to the requirements of the protocol.	Discontinuation from Treatment and Trial
The subject is no longer able to participate in the trial or is not compliant with trial-related procedures.	Discontinuation from Treatment and Trial
The subject takes a prohibited treatment during the trial.	This deviation should be documented and consulted

	regarding the management of the subject.
Subjects who report suicidal ideation with intent, with or without a plan or method (i.e., a positive response to items 4 or 5 in the assessment of suicidal ideation on the C-SSRS) or suicidal behavior may meet discontinuation criteria.	Please refer to Section 7.1.2.2.11, 7.2.3.2 and the ECI guidance document for details.

Discontinuation from treatment is “permanent.” Once a subject is discontinued, he/she shall not be allowed to restart treatment.

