7.1.1.2 Inclusion/Exclusion Criteria

If it is determined that the subject does not meet the inclusion/exclusion criteria at visits, the subject will be withdrawn from the study.

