7.1.4 Other Procedures

7.1.4.1 Withdrawal/Discontinuation

When a subject discontinues/withdraws from participation in the trial during visit 2 (before completing the three planned stimulations), all applicable activities scheduled for the end of visit 2, as outlined in Section 6.0 Trial Flow Chart, will be performed at the time of

discontinuation. Any adverse events which are present at the time of discontinuation/withdrawal will be followed in accordance with the safety requirements outlined in Section 7.2 - Assessing and Recording Adverse Events

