8.0 STATISTICAL ANALYSIS PLAN

8.1 Statistical Analysis Plan Summary

Considering this is the first study in a very small population for assessing the safety and tolerability and getting insights on the efficacy, results will be provided only as a descriptive statistical analysis

Table 5 Statistical analysis plan

Study Design Overview	Modulation of the motor pathway by Transcranial Pulse Stimulation in people with ALS: a pilot randomized trial
Treatment Assignment	Active stimulation: 36,000 pulses in 2 weeks distributed in 6 sessions Sham: stimulations using a sound blocker (membrane filled with air)
Analysis Populations	Intention to treat Per Protocol
Primary Endpoint(s)	Stage 1. Change in the motor cortex excitability threshold from baseline to week 8. Stage 2. Change from baseline to month 6 in the ALS functional rating scale-revised (ALSFRS-R) total score.
Key Secondary Endpoints	Secondary stage 1: 1. Change in the motor cortex excitability (paired-pulse transcranial magnetic stimulation (ppTMS): motor evoked potential (MEP) amplitudes, resting motor threshold, intra-cortical facilitation (ICF) and short intracortical inhibition (SICI)), from baseline to week 4 2. Change plasma NfL levels from baseline to week 4 and 8 3. Changes in muscle strength, assessed by MRC sum score from baseline to week 4 and 8 4. Changes in hand-held dynamometry from baseline to week 4 and 8 Secondary stage 2: 1. Differences (treated vs sham) and change (from baseline to end of the study (month 6)) in the slow vital capacity (SVC) 2. Differences (treated vs sham) and change (from baseline to end of the study (month 6)) in plasma NfL levels or other biomarkers from exploratory stage 1 if found significant

	
3. Differences (treated vs sham) and change (from baseline to end of the study (month 6)) in cortical hyperexcitability (MEP amplitudes, resting motor threshold, ICF and SICI)
 
4. Changes in muscle strength, assessed by MRC sum score from baseline to end of the study (month 6)
 
5. Changes in hand-held dynamometry, from baseline to end of the study (month 6)

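### Table 2 takes non-compliant patients out of the trial as well as off treatment, creating avoidable missing month-6 ALSFRS-R outcomes for the intention-to-treat analysis

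*Protocol*

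**What the plan says.** Section 5.8 states that Table 2 gives "reasons why a subject must be discontinued from treatment but may continue to be monitored in the trial", and also reasons for leaving both treatment and trial. The table has five rows:

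- Row 1, consent withdrawn: "Discontinuation from Treatment and Trial".
- Row 2, a medical condition or personal circumstance that in the investigator's opinion creates unnecessary risk or prevents adherence: the same action.
- Row 3, "The subject is no longer able to participate in the trial or is not compliant with trial-related procedures": the same action.
- Row 4, a prohibited treatment: the deviation is documented and advice is sought.
- Row 5, suicidal ideation with intent, or suicidal behavior: a referral to other sections.

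The text above the table adds that "a subject may be withdrawn by the investigator if enrollment into the trial is inappropriate, the trial plan is violated", among other grounds.

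Section 7.1.4.1 deals with a patient who leaves during visit 2 and asks for "all applicable activities scheduled for the end of visit 2, as outlined in Section 6.0 Trial Flow Chart", done at the time of discontinuation. Section 7.1.1.2 says of a patient found at visits not to meet the entry criteria that "the subject will be withdrawn from the study". Section 5.9 plans no replacement.

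In section 8.1, Table 5 lists the analysis populations as "Intention to treat Per Protocol", the Stage 2 primary endpoint as the change in ALSFRS-R total score from baseline to month 6, and the method as ANCOVA.

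**The concern.** An intention-to-treat comparison uses the outcome of every randomized patient, whether or not the patient kept to the treatment. That requires the outcome to be collected after treatment stops. Row 3 makes poor compliance a reason to stop collecting it. The introductory sentence shows that the protocol meant to keep some patients under observation after treatment stopped, but the table never does so.

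The missing values are unlikely to be a random subset. The protocol describes ALS as a progressive loss of motor function (section 4.1.1), and the visits require attendance and physical testing (section 6.0). Failure to comply may therefore go with faster decline. A statistical analysis plan can choose a method for missing data, but it cannot recover scores that the protocol stopped collecting.

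**Working it through.** **1. Is there a treatment-only route?** The sentence before the table promises that some patients "must be discontinued from treatment but may continue to be monitored in the trial". Rows 1, 2 and 3 end both treatment and trial. Row 4 states neither. Row 5 refers elsewhere, and the C-SSRS text (section 7.1.2.2.5) ends trial participation for those not cleared to continue. The promised action is in none of the five rows.

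**2. Is month 6 recovered elsewhere?** Section 7.1.4.1 covers leaving during visit 2 and sets assessments at that moment only. Section 7.1.2.1.1 adds a physical and neurological examination at early discontinuation. Neither gives a month-6 ALSFRS-R. Scores from before removal do remain: the Stage 2 flow chart lists the ALSFRS-R at visits 1, 2, 3-5, 6-7 and 8.

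**3. The protocol's own power figure.** Section 8.9 states 90% power at alpha 0.05 with 6 patients per arm. It gives no effect size, SD, sidedness or dropout allowance, so the figure cannot be reproduced, only inverted. With a two-sided test and the normal formula, the implied effect is (1.960 + 1.282) × √(2/6) = 1.87 SD; with the t distribution it is 2.08 SD. The present point does not depend on this figure, and it says nothing about losses.

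**4. Loss of precision (illustration).** Assumptions: two-sided 0.05 t-test; removal of 10%, 20% or 30%, none of which is in the protocol; reference effect d chosen to give 80% power when all 40 patients have outcomes. Power comes from the noncentral t with n1 + n2 − 2 degrees of freedom and noncentrality d / √(1/n1 + 1/n2). Both allocation ratios are shown because the synopsis says 2:1 and section 5.3 says 1:1.

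| Removed | 2:1, d = 0.97 SD | 1:1, d = 0.91 SD |
|---|---|---|
| 0% | 27/13: 80% | 20/20: 80% |
| 10% | 24/12: 76% | 18/18: 76% |
| 20% | 22/10: 69% | 16/16: 70% |
| 30% | 19/9: 64% | 14/14: 64% |

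Each removal costs 1/40 = 2.5% of the randomized sample.

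**5. Selection (illustration).** Let a share r of an arm be removed, and let those patients decline k SD more than the rest of that arm. If the rest have mean change m, the full arm has mean (1 − r)m + r(m − k) = m − rk. The completers' mean is m, so decline is understated by rk.

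- Removal in one arm only: the comparison is biased by rk in favor of that arm. With r = 0.2 and k = 1 this is 0.2 × 1 = 0.2 SD; with r = 0.1 and k = 0.5 it is 0.05 SD.
- The same r and k in both arms: the two shifts cancel, so there is no bias between arms, but decline in each arm is understated by rk.

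**The case against.** **The analysis is still possible.** A reader might infer that the rule makes the intention-to-treat analysis impossible. The documents do not support that. Removed patients remain randomized, their earlier ALSFRS-R scores remain, and a missing-data method may be set out in an analysis plan that is not shown. This stands, and it limits the point to avoidable missing outcomes.

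**No particular bias can be stated.** A reader might also infer a spurious benefit of a definite number of points. That needs a removal rate, a link with decline and a difference between arms, and the protocol gives none of these. It describes stimulation as producing no perceived sensation, side effects as headache or fatigue passing within 24-48 hours (sections 4.1.2 and 4.1.3), and blinding of patient and physician (section 5.2.3). These give no particular reason to expect unequal removal. This stands.

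**Section 7.1.1.2 may not reach randomized patients.** It could be read as removing patients whose slow vital capacity falls below 50% during follow-up. But the Stage 2 flow chart lists eligibility only at Visit 1, and slow vital capacity only at visit 2 and at the start of the open-label extension. A fall would not be seen at any scheduled visit between baseline and the end of the blinded period. The wording is loose, and section 7.1.1.9 adds to this by screen-failing patients at Visit 4, after randomization at Visit 2. Continuous removal of progressing patients is nevertheless only one interpretation.

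**Some loss would occur anyway.** Row 3 also covers patients no longer able to take part, and many of them would miss month 6 under any wording. Section 5.5 speaks of stopping trial therapy, rather than leaving the trial, when a prohibited treatment is indicated. Both are fair, but neither covers a non-compliant patient who could still attend.

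**This is a pilot.** The sample is called exploratory, and section 8.1 promises descriptive results only, although Table 5 names ANCOVA. That lowers the stakes but does not remove the contradiction.

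**Conclusion.** The point holds in a limited form. Section 5.8 contradicts its own table, and row 3 ends outcome collection for patients who could still be assessed. That creates avoidable, adherence-related gaps in the Stage 2 primary endpoint and leaves the named intention-to-treat analysis dependent on assumptions that the data cannot check.

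The size cannot be derived from the protocol. The fall in power to about 76% to 64% rests on assumed removal of 10% to 30%. Bias between arms requires removal that differs by arm and is related to decline; with equal removal the main effects are understated decline and lost precision.

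Separately, the flow chart ends the blinded period at week 16 and then opens the extension, which puts the month-6 randomized outcome in doubt even for fully compliant patients. That needs its own correction and does not cure this one.

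**What to change.** Before Stage 2 randomization:

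1. Reconcile the sentence introducing Table 2 with the actions in the table. Leave unchanged when treatment stops.
2. For non-compliance (row 3), state separately whether treatment stops and whether outcome collection stops. Patients who still consent and are able to attend should continue the already scheduled ALSFRS-R and safety assessments to the primary time point.
3. Leave withdrawal of consent (row 1) and the investigator's safety-based withdrawal (row 2) as they are. Keeping patients judged to be at risk in study visits is not proposed.
4. Clarify that the withdrawal in section 7.1.1.2 concerns eligibility before randomization, in line with the flow chart, and align section 7.1.1.9 with it.

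The cost is protocol wording and a few extra visits for patients off treatment.

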5.9 Subject Replacement Strategy

No subject replacement is intended.

5.10 Beginning and End of the Trial

The overall trial begins when the first subject signs the informed consent form. The overall trial ends when the last subject completes the last study-related phone-call or visit, discontinues from the trial, or is lost to follow-up (i.e., the subject is unable to be contacted by the investigator).

5.11 Clinical Criteria for Early Trial Termination

There are no pre-specified criteria for terminating the trial early.

6.0 TRIAL FLOW CHART

Table 3 Trial flow chart

Stage 1 Visit Number	1	2	3-5	6
Visit Title	Screen	Baseline	Stimulation	End
Scheduled Week	0	1	2-3	4
Scheduling Window by Days:	3	3	2	5
Administrative Procedures				
Informed Consent	X			
Inclusion/Exclusion Criteria	X			
Identification Card	X			
Medical History	X			
Prior Medication Review	X			
Monitor Trial Device Compliance		X	X	
Clinical Procedures Assessments				
TPS stimulations	X	X	X	
Vital Signs		X	X	X
Physical Exam		X	X	X
MRC sum score		X	X	X
Hand-held dynamometry		X	X	X
Brain MRI		X		
TMS		X		
Neurological examination	X	X	X	X
C-SSRS	X	X	X	
ALSFRS-R	X	X	X	X
Blood draw		X	X	X
SVC		X		

Stage 2 Visit Number	1	2	3-5	6-7	8	9	10-16	17-18	19
Visit Title	Screen	Rand Base	Stim	Stim FU	End DBP	Onset OLE	Stim 3	Stim FU	End OLE
Scheduled Week	0	1	2-3	8-16	16	16	16-18	26-34	34
Scheduling Window by Days:	3	3	2	2	5	7	2	2	5
Administrative Procedures									
Informed Consent	X								
Inclusion/Exclusion Criteria	X								
Identification Card	X								
Medical History	X								
Prior Medication Review	X								
Monitor Trial Device Compliance		X	X	X			X	X	
Clinical Procedures Assessments									
TPS stimulations	X	X	X	X			X	X	
Vital Signs		X	X	X	X	X	X	X	X
Physical Exam		X	X	X	X	X	X	X	X
MRC sum score		X	X	X	X	X	X	X	X
Hand-held dynamometry		X	X	X	X	X	X	X	X
Brain MRI	X								
TMS	X	X	X	X	X				
Neurological examination	X	X	X	X	X	X	X	X	X
C-SSRS	X	X	X	X			X	X	
ALSFRS-R	X	X	X	X	X	X	X	X	X
Blood draw		X	X	X	X				
SVC		X				X			

Stim: TPS stimulation (6 times in 2 weeks, 20 min each); rand: randomization; Base: baseline; DBP: double blind period; OLE: Open Label Extension

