4.1.2. TPS neuromodulation therapy

The TPS neuromodulation device (NEUROLITH) is a medical device for offline MRI-guided neuromodulation treatment that maintains brain region specific targeting based on a neuronavigation system using an electromagnetic TPS system (**figure 3**). The Neurolith system has been approved in Europe (CE mark) in 2018 for the treatment of Alzheimer disease. At present, around 10,000 patients with Alzheimer disease have been exposed to TPS with excellent safety. No serious adverse events have been reported and the most common adverse events are headache or fatigue that disappear in 24-48h. The device directly delivers the ultrashort sound beam to a key structure involved with motor modulation such as M1 cortex using a neuronavigation system (figure 2). The NEUROLITH device will be comfortably applied at the clinic visit where the patient remains sited, the hair will be humidified, and ultrasound gel is applied to the electromagnetic stimulator. The device produces a characteristic sound that is not disturbing but recognized. No heat, pain, numbness or any other sensation is perceived by the patient. The system provides a sham stimulation option based in the use of a membrane containing gas that blocks sound transmission, preserving the characteristic sound or any other feature the patient may notice.

Prior to first use, every subject will undergo an MRI scan to register the location on their temple region relative to the brain targets for tailored anatomical registration (**figure 4 and 5**). NEUROLITH has an external control unit containing a battery supply for initial cost efficiency, flexibility in stimulation protocols and human clinical study designs.

Fig.3. Neurolith device is composed by the stimulation system (control unit and power source) and neuronavigation system

Fig.4. The neuronavigation system guides TPS stimulation using off-line MRI guidance

The stimulation involves delivering 1,000 pulses per cortical region, with a maximum of 6,000 pulses per session¹³. The system uses a low energy flux density maximum of 0.25 mJ/mm² accordingly with EMA and FDA guidelines (high energy is defined as > 0.5 mJ/mm²). Each session use to extend for 20 min. The standard therapy involves 6 sessions in 2 weeks. After completion, single follow-up sessions are applied every 2 months.

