7.1.5.1.1 Visit 1: Screening, brain MRI, TMS and SVC

At Visit 1, subjects who provide informed consent will undergo a series of diagnostic and safety assessments to determine if they are eligible for the trial. A designated subject must also consent to participate and will be asked to complete certain assessments throughout the trial. Subjects planning to undergo elective procedures during the study (known prior to trial start) should not proceed until such procedures have been completed.

At the screening visit, medical history, use of drugs, alcohol, caffeine, smoking will be recorded. In addition urine test and the Columbia-Suicide Severity Rating Scale (C-SSRS) will be administered. The SVC will be collected by spirometry.

If the subject fulfills the inclusion criteria and signs the informed consent, a brain MRI and a TMS study will be scheduled in the following 2-7 days (always before Visit 2). Once obtained the brain MRI, it will be uploaded to the TPS device for neuronavigation purposes. TMS will be conducted for defining presence of hyper-excitability.

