7.1.5.1.2 Visit 2: baseline

Patients will be randomized to either treatment or sham stimulation and assigned a code (except for patient sin stage 1, which are not randomized, and all receive active stimulation). Before starting stimulation, the researcher will conduct a vital signs, physical exam and neurological examination. Urine (50 ml) and blood (20 ml) will be collected and stored. Then, the patient will be subjected to the first TPS stimulations (a 20 min stimulations).

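### Both flow charts tick TPS stimulation at the Screening visit, where no text section places one, and chart, visit text and synopsis need one first-stimulation visit per stage

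*Protocol*

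**What the plan says.** Section 6.0 has one chart per stage. In each, "TPS stimulations" is ticked at Visit 1 (Screen, week 0), at Visit 2 and at Visits 3-5. The Stage 2 row continues through the follow-up and open-label stimulation visits.

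The text differs:

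- Section 7.1.5.1.2 (Visit 2: baseline) describes randomisation for Stage 2, then examinations and samples, and continues: "Then, the patient will be subjected to the first TPS stimulations". It also requires that "Before starting stimulation, the researcher will conduct a vital signs, physical exam and neurological examination".
- Section 7.1.5.1.1 (Visit 1) covers consent, history, C-SSRS, urine test and spirometry, with no stimulation. It schedules MRI and TMS two to seven days later, before Visit 2, and adds: "Once obtained the brain MRI, it will be uploaded to the TPS device for neuronavigation purposes".
- Section 4.1.2: "Prior to first use, every subject will undergo an MRI scan".
- Section 5.2.2 times treatment from randomisation. Section 7.1.1.9 puts randomisation at Visit 2, once eligibility is confirmed.
- The synopsis schedule (Section 1.0) lists stimulation at V2 for Stage 1. For Stage 2 it lists randomisation and baseline at V2 and stimulation at V3-5.

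**The concern.** The flow chart is an instruction to sites. Section 2.1 refers the reader to it for the prescribed times of procedures, and Section 7.1.5.1 says each visit should be performed as the chart notes. A tick at Screening therefore tells staff to deliver a stimulation that the visit text does not contain.

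Four things would be at stake if it were followed:

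- **Eligibility.** A patient could be stimulated before the entry criteria on SVC and cortical hyperexcitability had been verified.
- **Baseline.** Every endpoint is a change from baseline. A baseline first taken at Visit 2 would then be measured after a stimulation.
- **Allocation.** In Stage 2 no arm exists at Visit 1. The procedure in Section 5.2.3, in which an independent investigator sets the device to active or sham by arm, could not be carried out.
- **Accounting.** Section 7.1.1.8 ties treatment accounting to the chart, and the row "Monitor Trial Device Compliance" is blank at Visit 1, so the session would go unrecorded there.

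**Working it through.** No sample size or power figure is involved. The check is a cell-by-cell reading of the charts, set against the text.

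**Step 1: is the tick really in the Visit 1 column?** The tables were extracted from PDF, so a column shift has to be excluded.

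| Row | Stage 1 ticks | Stage 2 ticks |
|---|---|---|
| TPS | 1, 2, 3-5 | 1, 2, 3-5, 6-7, 10-16, 17-18 |
| Device compliance | 2, 3-5 | 2, 3-5, 6-7, 10-16, 17-18 |
| Vital signs | 2, 3-5, 6 | 2 onward, all visits |
| C-SSRS | 1, 2, 3-5 | 1, 2, 3-5, 6-7, 10-16, 17-18 |

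Neighbouring rows keep their blank at Visit 1. The Stage 2 TPS row is correctly blank at Visits 8, 9 and 19, the end and onset visits. Moving the Stage 1 row one column to the right would put a stimulation at the End visit. The row is aligned, and the Visit 1 tick is additional to the pattern of the compliance row in both charts.

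**Step 2: could the tick be there to complete the session count?** Section 5.2.1 gives 6 sessions in the first two weeks. Assuming one session per visit, Visits 1, 2 and 3-5 give 1 + 1 + 3 = 5. Without Visit 1 the count is 1 + 3 = 4. Neither equals 6, so the tick does not reconcile the chart with the regimen.

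**Step 3: where does each part of the protocol put the first stimulation?**

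| Source | Stage 1 | Stage 2 |
|---|---|---|
| Section 6.0 charts | Visit 1 | Visit 1 |
| Section 7.1.5.1.2 | Visit 2 | Visit 2, after randomisation |
| Synopsis | V2 | V3-5 |
| Sections 5.2.2 and 7.1.1.9 | not applicable (no randomisation) | after randomisation at Visit 2 |

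For Stage 1 there are two answers. For Stage 2 there are three.

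**Step 4: what would a Visit 1 stimulation precede?**

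- *Both stages, by the charts:* the first blood draw (plasma NfL and vesicle biomarkers), MRC sum score, dynamometry, SVC, vital signs and physical examination, all first ticked at Visit 2.
- *Stage 1, by the chart:* TMS, ticked only at Visit 2. This is the measure behind the Stage 1 primary endpoint.
- *MRI:* the Stage 1 chart ticks it at Visit 2, but the Stage 2 chart ticks it at Visit 1, in the same column as the TPS tick. For Stage 2, the statement that stimulation would come before MRI rests on Sections 4.1.2 and 7.1.5.1.1, not on the chart.
- *ALSFRS-R (both stages) and Stage 2 TMS:* ticked at Visits 1 and 2. Whether these baselines are affected depends on the order of procedures within Visit 1 and on which value is used as baseline.
- *Eligibility:* by the charts, SVC is outstanding at Visit 1 in both stages, and TMS as well in Stage 1. By the text, SVC is done at Visit 1 but TMS is outstanding. On either reading at least one entry criterion is still open.
- *Randomisation:* Stage 2 only.

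**The case against.** The strongest reply is that this is a charting slip that the rest of the protocol overrides. Section 7.1 says the chart summarises procedures that are described in detail afterwards. The device needs an uploaded MRI, which the text obtains after Visit 1. In Stage 2 it also has to be set by arm. The TPS row has exactly the same pattern as the C-SSRS row in both charts, which is consistent with a copied row, though that is an inference. Staff may well notice. All of this stands, and it makes the harm conditional. It does not remove the contradiction, because Section 7.1.5.1 directs sites to the chart.

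It can also be said that the Stage 1 baseline argument leans on the chart's own TMS tick. The synopsis lists TMS at V1, and Section 7.1.5.1.1 puts it between Visits 1 and 2. That is fair: the Stage 1 TMS baseline is at risk under the chart, and under the text only if a Visit 1 stimulation were added to it.

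A reader might go further and infer that all 10 + 40 = 50 patients are affected, or that sham patients would receive 1 of the 6 + 2 = 8 sessions in Section 5.2.1 (12.5%), so that the primary comparison is diluted by a known amount. The documents do not support this. No patient is affected where the visit text is followed. The 12.5% assumes that the Visit 1 session is active and is one of the eight. If it were an extra active session for everyone, the arms would receive 9 and 1, and the difference would still be 8. No dose-response figure is given, so a share of sessions is not a measure of bias.

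**Conclusion.** The point holds as an internal inconsistency. Both flow charts schedule a stimulation at Visit 1 that no text section contains, and for Stage 2 the chart, the visit text and the synopsis give three different first-stimulation visits. Aligning the chart with Section 7.1.5.1.2 alone would leave the conflict with the synopsis in place.

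The consequence is conditional: a site that followed the chart would stimulate before eligibility is confirmed, before the measures first charted at Visit 2 and, in Stage 2, before allocation. The size of any resulting bias cannot be computed from the document. The conclusion assumes only that the extracted tables reproduce the ticks correctly, which the alignment check supports. It should be corrected because the chart is the operative schedule and the correction is cheap. It is not evidence that a stimulation before randomisation is planned.

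**What to change.** Reconcile the two charts in Section 6.0 with Sections 7.1.5.1.1, 7.1.5.1.2 and 5.2.2 and with the synopsis schedule, so that all of them give the same first-stimulation visit for each stage. Then check that this visit agrees with the order the protocol itself sets out: eligibility confirmed, baseline measures taken and, in Stage 2, randomisation done. While doing so, check the number of stimulation visits in the charts against the six-session period in Section 5.2.1. Which visit is chosen is for the sponsor and investigator to settle.

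The cost is an edit to the charts and, where they differ, to the synopsis or visit text. Sample size and analysis method are untouched.
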